Discontinuation or interruption of trilaciclib or placebo + E/P does not preclude continuation of atezolizumab and vice versa. For instance, if an AE is attributed to trilaciclib or placebo, etoposide, or carboplatin (eg, hematologic toxicity) during the induction part of the study; then atezolizumab will be continued while the trilaciclib or placebo + E/P are held. While the trilaciclib or placebo + E/P are held, the patient will continue to receive atezolizumab, be monitored for safety (see Section 10.3.4), and will begin the next trilaciclib or placebo + E/P/A-containing induction cycle after the toxicity resolves. If the AE is immune related and attributed to atezolizumab; then trilaciclib or placebo + E/P will be continued for up to 4 cycles while the atezolizumab is held.

After discontinuation of all study drugs, patients should be strongly encouraged to complete all scheduled assessments through the end of their current 21-day treatment cycle, [REDACTED] CBC assessment on Day 22; all Post-Treatment Visits; and the Survival Follow-up Phase of the study, which is to continue until at least 70% of the patients on the study have died. The G1T28-05 study will be completed when the Survival Follow-up Phase has been completed, or upon sponsor termination of the study.

The total study duration is at least 36 months, assuming 12 months of accrual and 24 months follow-up.

The Survival Follow-up Phase will continue until at least 70% of the randomized patients have died.

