### Dose Modifications for Hematologic Toxicity

#### First Day of Induction Cycle 2 and Beyond

In order to start Induction Cycle 2 and subsequent induction cycles as scheduled, on Day 1 of the cycle, patients must have an ANC  $\geq 1.5 \times 10^9/L$ , platelet count  $\geq 100 \times 10^9/L$ , and nonhematologic drug-related toxicities (except alopecia) must be  $\leq$  Grade 1 or have returned to baseline. The dose adjustments in [Table 8-2](#) are based on the ANC and platelet counts on the first day of treatment for Cycle 2 and each subsequent induction cycle.

**Table 8-2 Etoposide and Carboplatin Dose Adjustments Based on Lack of Recovery of Absolute Neutrophil or Platelet Counts on the First Day of Induction Cycle 2 and Each Successive Cycle**

Absolute Neutrophil Count <math>< 1.5 \times 10^9/L</math>	Etoposide	Carboplatin
First episode	No change. Use G-CSF with subsequent cycles. Refer to the American Society of Clinical Oncology (ASCO) guidelines (Smith 2015).	No change. Use G-CSF with subsequent cycles. Refer to ASCO guidelines (Smith 2015).
Second episode	First dose reduction	First dose reduction
Third episode	Second dose reduction	Second dose reduction
Fourth episode	Discontinue drug	Discontinue drug
Platelet Count <math>< 100 \times 10^9/L</math>	Etoposide	Carboplatin
First episode	First dose reduction	First dose reduction
Second episode	Second dose reduction	Second dose reduction
Third episode	Discontinue drug	Discontinue drug

G-CSF = granulocyte colony-stimulating factor

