#### 10.3.4. **Atezolizumab Administration While Trilaciclib or Placebo + E/P Is Held**

During the induction part, interruption or delay of trilaciclib or placebo + E/P does not preclude continuation of atezolizumab and vice versa. If the AE is immune related and attributed to atezolizumab, then trilaciclib or placebo + E/P will be continued for up to 4 cycles while atezolizumab is held. If an AE is attributed to trilaciclib or placebo, etoposide, or carboplatin (eg, hematologic toxicity) during the induction part of the study, then atezolizumab will be continued every 21 days while trilaciclib or placebo + E/P are held. During the period in which trilaciclib or placebo + E/P are held and atezolizumab is continued, patients should be monitored as follows prior to administering atezolizumab every 21 days:

- ECOG performance status evaluation
- Physical examination
- Weight and vital signs measurements
- Clinical chemistry, hematology, and urinalysis tests (note: clinical chemistry and urinalysis tests may be obtained up to 72 hours prior to the first dose of each cycle of study treatments, and hematology tests may be obtained up to 24 hours prior to the first dose of each cycle of study treatments). The clinical chemistry and hematology results should be reviewed before dosing.
- FACT-L and FACT-An Questionnaires

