Study drug administration will continue for up to 4 chemotherapy-containing (trilaciclib or placebo + E/P/A) cycles during the induction part of the study and atezolizumab monotherapy will be administered on Day 1 of every 21-day cycle during the maintenance part of the study. Study drug administration will continue until disease progression per RECIST v1.1, unacceptable toxicity, withdrawal of consent, or discontinuation by investigator, whichever occurs first. However, if the patient appears to be deriving clinical benefit, the investigator believes it is in the best interest of the patient, and the patient has provided re-consent, study drug administration may be continued until loss of clinical benefit (see Section 11.1.4). Treatment cycles will occur consecutively without interruption, except when necessary to manage toxicities or for administrative reasons as described below.

Criteria for Starting Cycle 2 and subsequent cycles in the induction part up to Induction Cycle 4

Patients must meet all of the following criteria:

- Absolute Neutrophil Count (ANC) $\geq 1.5 \times 10^9/L$
- Platelet count $\geq 100 \times 10^9/L$
- Nonhematologic drug-related toxicities (except alopecia) must be \leq Grade 1 or have returned to baseline

A delay of > 9 weeks for recovery from any toxicity related to trilaciclib or placebo + etoposide and carboplatin (E/P) in order to meet the continuation criteria will result in discontinuation of trilaciclib or placebo + E/P. A delay of > 15 weeks for recovery and management of immune-related toxicities attributed to atezolizumab (12 weeks for recovery to \leq Grade 1 and up to an additional 3 weeks for steroid taper of oral prednisone or equivalent to ≤ 10 mg/day) will result in discontinuation of atezolizumab. If patients meet the criteria for starting the subsequent cycle, a delay of up to 2 weeks is permitted for administrative reasons (eg, holiday, vacation, etc.);

however, a total delay of more than 9 weeks for trilaciclib or placebo + E/P, or 15 weeks for atezolizumab must be discussed with the medical monitor. [REDACTED]

[REDACTED]

[REDACTED]

[REDACTED]

[REDACTED]

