Discontinuation or interruption of trilaciclib or placebo + E/P does not preclude continuation of atezolizumab and vice versa. For instance, if an AE is attributed to trilaciclib or placebo, etoposide, or carboplatin (eg, hematologic toxicity) during the induction part of the study; then atezolizumab may be continued while the trilaciclib or placebo + E/P are held. While the trilaciclib or placebo + E/P are held, the patient will continue to receive atezolizumab, be monitored for safety, and will begin the next trilaciclib or placebo + E/P/A-containing induction cycle after the toxicity resolves. If the AE is immune related and attributed to atezolizumab; then trilaciclib or placebo + E/P may be continued for up to 4 cycles while the atezolizumab is held.

After discontinuation of all study drugs, patients should be strongly encouraged to complete all scheduled assessments through the end of their current 21-day treatment cycle, [REDACTED]; CBC assessment on Day 22; all Post-Treatment Visits; and the Survival Follow-up Phase of the study, which is to continue until at least 70% of the patients on the study have died. The G1T28-05 study will be completed when the Survival Follow-up Phase has been completed, or upon sponsor termination of the study.

- The total study duration is at least 36 months, assuming 12 months of accrual and 24 months follow-up.
- The Survival Follow-up Phase will continue until at least 70% of the randomized patients have died.

The study scheduled assessments are presented in [Table 2](#) below:

Table 2 Schedule of Assessments

Cycle Day	Screening	Enroll	Induction (21-day cycles) ^a										Last Induction Cycle	Maintenance (21-day cycles) ^b		Post-Treatment Visits ^c		Survival Follow-up ^d
			Induction Cycles 1 and 3					Induction Cycles 2 and 4						Maintenance Cycle 1 and Odd Cycles	Maintenance Cycle 2 and Even Cycles	30 (+3)	90 (+7)	
	-14	-3 to 1	1	2	3	8	15	1	2	3	8	15	22	1	1	30 (+3)	90 (+7)	
Informed Consent ^e	X																	
Demographics	X																	
Medical History ^f	X																	
Eligibility Eval.	X	X																
Performance Status	X		X					X						X	X	X	X	
Physical Exam	X		X					X						X	X	X	X	
Height, Weight & Vital Signs ^g	X		X		X			X		X				X	X	X	X	
Electrocardiogram	X												X					
Clinical Chemistry	X		X ^h					X ^h						X ^h	X ^h	X	X	
TSH, free T4, and free T3	X							X							X	X	X	
Hematology	X		X ⁱ		X	X	X	X ⁱ		X	X	X	X	X ⁱ	X ⁱ	X	X	
Urinalysis	X		X ^h					X ^h						X ^h	X ^h	X	X	

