5. PRIMARY AND SECONDARY ENDPOINTS

The following general definitions will be applied to all endpoints derivation unless otherwise specified.

Term	Definition
Severe Neutropenia (SVN)	ANC lab value that meets the common terminology criteria for adverse events (CTCAE) criteria for \geq Grade 4 toxicity
Cycle baseline	The last non-missing value within the window starting from 3 days prior to the date/time of study drug administration on Day 1 of Cycle 1 and 1 day prior to Day 1 of each subsequent cycle (i.e. Cycle 2, Cycle 3, etc.); must be prior to the time of study drug administration
Cycle nadir	The lowest value for a given hematologic parameter that occurs between start of cycle and end of cycle and is less than the cycle baseline.
Duration of cycle	Total number of days from start of cycle to end of cycle, that is, date of end of a cycle - date of start of cycle + 1.
End of cycle*	Day 1 of the subsequent cycle. For example, the end of cycle for Cycle 1 is Day 1 of Cycle 2. For the last induction cycle (where no subsequent maintenance cycle is given), the end of cycle will be defined as Day 36 after the first dose of the cycle. For the last maintenance cycle, the end of cycle will be defined as Day 30 after the first dose of the cycle.
Start of cycle	Day 1 of each cycle starts with the administration of study drug(s) (etoposide, carboplatin, atezolizumab, or trilaciclib)
Start of study	Date of randomization
Study baseline	The last non-missing value prior to, or on the date of administration of study drug(s) (etoposide, carboplatin, atezolizumab, or trilaciclib); must be prior to the time of study drug administration
Change from baseline	Calculated as the post-baseline value minus the baseline value. If the baseline value is missing for a particular endpoint, change from baseline will be missing.
Induction treatment period	Between the date of randomization and end of cycle for the last Induction cycle.
Maintenance treatment period	Between the date of Day 1 of the first maintenance cycle and end of cycle for the last Maintenance cycle.
Overall treatment period	Between the date of randomization and end of cycle for the last cycle.

* For various hematologic parameter analyses, the last assessment prior to end of cycle will be utilized in the analyses. Situations where this applies will be indicated as such.

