5.2.1.2. Number of Cycles Received

Patients are considered to have started a cycle if they have received at least one dose of any study drug (carboplatin, etoposide, atezolizumab or trilaciclib). In addition to the numeric summary for the number of cycles, the number of cycles for the induction treatment period will be categorized as 1, 2, 3 or 4. The number of cycles in the maintenance period will be categorized as: 1, 2, 3, 4, 5, 6, and > 6.

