5.2.1.4. Modifications of Study Therapy, Including Cycle (Dose) Delay, Missed Doses, Dose Interruptions, and Dose Reductions.

- After Cycle 1, patients need to meet pre-specified laboratory parameter criteria before initiating Cycle 2 and each subsequent cycle of chemotherapy. A “Cycle Day Status” page asks if the cycle was delayed. If the start of the current cycle was delayed (the site

answers “Yes”), this will be counted as a delay. Reason for delay is not collected. Delays will be calculated over the induction, maintenance, and overall periods.

- Missed doses are identified on the dosing page of each study drug based on the question “Was the dose given?”. The missed dose information will be obtained for each study drug. For a study drug, if the last record of response to question “Was the dose given?” is No, it will not be considered as a missed dose but instead considered to be end of treatment if both criteria below are met
 - No other study drugs are given on the same day, and
 - No study drugs are given subsequently.

The reasons for missed doses will be summarized in the following categories: (1) Hematological toxicity, (2) Non-hematological toxicity, and (3) Other.

- Dose reductions are not permitted for trilaciclib or atezolizumab.
- Dose reductions for carboplatin and etoposide are determined by comparing the actual dose on the respective drug administration pages between the current cycle and the previous cycle. A window of 10% around both etoposide and carboplatin doses will be used to check for dose reductions. They occur in the following order:
 - 1st Reduction: Etoposide dose reduced from 100 mg/m² to 75 mg/m², Carboplatin dose reduced from AUC 5 to AUC 4.
 - 2nd Reduction: Etoposide dose reduced to 50 mg/m², Carboplatin dose reduced to AUC 3.

No more than 2 dose reductions of E/P in total are allowed for any patient. Toxicity that requires dose reduction more than twice will lead to discontinuation of trilaciclib or placebo + E/P therapy; discontinuations will not be counted as a dose reduction. All dose reductions for toxicity are permanent, and no dose increases are allowed when dose reductions are made for toxicity.

- Dose interruptions for all drugs are also captured on the dosing page and will be summarized for each study drug.

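### The SAP's any-dose cycle rule conflicts with its own four-cycle, chemotherapy-containing induction when atezolizumab is given alone during an etoposide/carboplatin hold (minor)

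*SAP*

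**What the plan says.** **Rules under which atezolizumab alone starts a cycle.** SAP 5.2.1.2 says that patients are "considered to have started a cycle if they have received at least one dose of any study drug (carboplatin, etoposide, atezolizumab or trilaciclib"). The definitions table in SAP section 5 says that "Day 1 of each cycle starts with the administration of study drug(s) (etoposide, carboplatin, atezolizumab, or trilaciclib"), and that a cycle ends on Day 1 of the next one.

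**Rules that treat an induction cycle as chemotherapy-containing.** Under Criteria for Subsequent Cycles and Study Duration, the SAP allows up to 4 chemotherapy-containing cycles and gives laboratory conditions headed "Criteria for Starting Cycle 2 and subsequent cycles in the induction part up to Induction Cycle 4". SAP 5.1.3.1 identifies the last induction cycle as the last one with placebo or trilaciclib plus E/P/A. SAP 5.2.1.2 itself has induction categories 1, 2, 3 and 4 only.

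**The situation in which they meet.** If an adverse event is attributed to trilaciclib/placebo or E/P during induction, Protocol 10.3.4 says "then atezolizumab will be continued every 21 days while trilaciclib or placebo + E/P are held". The SAP words this as "then atezolizumab may be continued while the trilaciclib or placebo + E/P are held". Under Protocol 6.1.1 the patient "will begin the next trilaciclib or placebo + E/P/A-containing induction cycle after the toxicity resolves".

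**How E/P reductions are derived.** SAP 5.2.1.4 finds them by "comparing the actual dose on the respective drug administration pages between the current cycle and the previous cycle", with a 10% window. SAP 5.1.2.3 speaks of changes in the protocol-specified dose and refers to section 5.2.1.4 for details... in the SAP's numbering, the exposure section that contains this algorithm. No visible text classifies an atezolizumab-only dose given during a hold.

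**The concern.** The hold dose and the dose reduction tend to arise from the same event. The adjustments in Protocol Table 8-2 "are based on the ANC and platelet counts on the first day of treatment for Cycle 2 and each subsequent induction cycle". Platelets below 100 × 10⁹/L on that day postpone E/P and, at the first episode, also order the first dose reduction. ANC below 1.5 × 10⁹/L does so from the second episode. Atezolizumab continues meanwhile. At E/P restart on a reduced dose, the any-dose rule makes the immediately preceding cycle one without E/P, and SAP 5.2.1.4 does not say what to compare with.

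All-cause dose reductions are H3, tested inside the multiplicity-controlled family. The number of induction cycles is the offset for H2 (occurrence of Grade 4 neutropenia), H3 and H5 (G-CSF administration), and the denominator of relative dose in Table 12. It also decides who counts as having completed 4 induction cycles in the sensitivity analyses of SAP 6.2.7.1.5, where three E/P cycles plus one hold dose could pass as four. Two programmers following the SAP could therefore derive different values from the same dosing records.

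**Working it through.** **Inputs.** Full dose per cycle is etoposide 3 × 100 = 300 mg/m² and carboplatin AUC 5 (Table 12). First-reduction levels are 75 mg/m² and AUC 4. A reduction is flagged when the dose falls below 90% of the comparator (the 10% window). Atezolizumab is given every 21 days during a hold, and the longest toxicity delay before E/P is discontinued is 9 weeks.

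**Cycle and reduction counts.** The SAP rules applied to example records (etoposide in mg/m²; hold = atezolizumab alone):

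| Record | Cycles, any dose | Cycles, E/P only | Reductions vs previous cycle, held dose missing | Same, held dose coded 0 | Reductions vs last cycle given |
|---|---|---|---|---|---|
| 100, 75, 75, 75 | 4 | 4 | 1 | 1 | 1 |
| 100, hold, 75, 75, 75 | 5 | 4 | 0 | 1 (the hold) | 1 |
| 100, hold, hold, hold, 75, 75, 75 | 7 | 4 | 0 | 1 (the hold) | 1 |
| 100, hold, 100, 100, 100 | 5 | 4 | 0 | 1 (false) | 0 |

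The SAP's maximum of 4 is reproduced in every row under E/P-only counting. The third row is the longest permitted single hold: 63/21 = 3 atezolizumab-only doses, so 4 + 3 = 7.

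**Offset.** For one hold dose the change is ln 5 − ln 4 = ln(5/4) = 0.223, so that patient's per-cycle rate is multiplied by 4/5 = 0.80. In the second row with the held dose missing, the patient enters H3 with 0 events over 5 cycles instead of 1 over 4.

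**Relative dose (Table 12), four full-dose E/P cycles plus one hold dose.**
- Etoposide: 100 × 1200/(300 × 5) = 80.0%, against 100 × 1200/(300 × 4) = 100.0%.
- Carboplatin: 100 × 20/(5 × 5) = 80.0%, against 100 × 20/(5 × 4) = 100.0%.

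Relative dose intensity divides by duration of exposure, so it does not change through the cycle count.

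**Scale for H2 (hold rates assumed).** The planning ratio is 0.11/0.45 = 0.244. Suppose every patient has 4 E/P cycles, 5% on trilaciclib have one hold dose, and 10% to 50% on placebo do. Ignoring covariates, the ratio is multiplied by the quotient of mean cycle counts: 0.244 × 4.10/4.05 = 0.247, up to 0.244 × 4.50/4.05 = 0.272.

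**H1, boundary case.** With Grade 4 counts on Days 15 and 22 and recovery on Day 29, duration is 22 − 15 = 7 days if the hold dose ends Cycle 1, and 29 − 15 = 14 days if E/P restart does. This needs Grade 4 neutropenia still present at about Day 22.

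**The case against.** The best answer is that the any-dose wording was never meant to open an extra induction cycle. Atezolizumab must be in both lists because both also cover maintenance, where it is the only drug. The specific text on induction (chemotherapy-containing, at most four, next E/P/A-containing cycle after recovery, categories ending at 4) should govern a general parenthesis. SAP 5.2.1.4 opens by requiring laboratory criteria before Cycle 2 and each later chemotherapy cycle. A dose given because those criteria failed can hardly be Cycle 2, so the previous cycle there would mean the previous chemotherapy cycle. The dose ladder in that section and the wording of SAP 5.1.2.3 would also let a programmer count a 75 mg/m² restart as the first reduction.

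Much of this stands: E/P-only counting is the likelier intention. It does not remove the conflict. The dosing pages ask drug by drug whether the dose was given, so one drug given and others missed on the same day is a foreseen record, and nothing overrides the explicit any-dose rule. If a site books the hold dose and the E/P restart in one cycle, no extra cycle arises, but the eCRF numbering is not in the documents.

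A reader might infer that the SAP as written always loses the reduction. It does not: the comparison is undefined, and the count is 0 or 1 depending on how the held dose is coded.

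**Conclusion.** The SAP contains two incompatible rules for what counts as an induction cycle, and its reduction algorithm has no comparator after a hold. For an affected patient this means 5 or more cycles instead of 4, an offset change of 0.223 for one hold dose, and relative dose of 80% instead of 100% when fully dosed. It also means a restart reduction that is missed, or a hold counted as a reduction, which is false if E/P restarts at full dose.

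A reader might go further and infer that the H3 ratio is biased in a known direction or loses a stated amount of precision. The documents do not support that: they give neither the frequency of hold doses nor the share of reductions that follow one, in either arm. Nor do they support a threat to the primary endpoints. The H2 shift is small under the assumed rates above, and H1 changes only in a boundary case. The effect on the trial result cannot be computed. Severity: minor.

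**What to change.** Amend two SAP rules before database lock:

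1. In section 5 and 5.2.1.2, count an induction cycle only if at least one dose of trilaciclib/placebo, etoposide or carboplatin is given. State that an atezolizumab-only dose during a hold neither starts nor ends an induction cycle. Keep the any-dose count for maintenance and for atezolizumab's own relative dose in Table 12.
2. In 5.2.1.4, compare each etoposide and carboplatin dose with the dose in the last cycle in which that drug was given.

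With these rules the second row of the table gives 4 cycles and 1 reduction, and the fourth row gives 4 cycles and 0 reductions. The cost is two sentences and the matching programming. The dosing data are already collected and no protocol change is needed.

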5.2.1.3. Dose Intensity and Cumulative Dose

Algorithms for calculating parameters relevant to the dose exposure and intensity are included in [Table 12](#). All doses, including unscheduled doses, will be used in the applicable parameter calculations. For trilaciclib/placebo, etoposide, and carboplatin, these drug specific calculations will be for induction period exposure only. For atezolizumab they will be for induction, maintenance, and overall exposure periods.

Table 12 Algorithms for Calculating Parameters Relevant to the Dose Exposure and Intensity

Parameter	Trilaciclib	Etoposide	Carboplatin	Atezolizumab*
Dosing schedule per protocol	240 mg/m ² IV on Days 1,2,3 of a 21-day cycle	100 mg/m ² IV on Days 1,2,3 of a 21-day cycle	AUC 5 IV on Day 1 of a 21-day cycle	1200 mg IV on Day 1 of a 21-day cycle
Dose by cycle	Total dose administered (mg) /most recent BSA (m ²) [(mg/m ²)]	Total dose administered (mg) /most recent BSA (m ²) [(mg/m ²)]	Total dose administered on Day 1 (Prescribed AUC and actual dose in mg)	Total dose administered (mg)
Cumulative dose	Sum of the doses administered to a patient in the duration of exposure, (mg/m ²)	Sum of the doses administered to a patient in the duration of exposure, (mg/m ²)	Sum of the doses administered to a patient in the duration of exposure (in total prescribed AUC)	Sum of the doses administered to a patient in the duration of exposure, (mg)
Dose intensity	Cumulative dose (mg/m ²) / (duration of exposure / 7) [(mg/m ² /week)]	Cumulative dose (mg/m ²) / (duration of exposure / 7) [(mg/m ² /week)]	Cumulative Dose (total prescribed AUC) / (duration of exposure / 7) [AUC/ week]	Cumulative Dose (mg) / (duration of exposure / 7) [(mg/week)]
Relative dose intensity (%)	100 * [Dose intensity (mg/m ² /week) / (720 /3 (mg/m ² /week)]	100 * [Dose intensity (mg/m ² /week) / (300 /3 (mg/m ² /week)]	100 * [Dose intensity (AUC/week) / (5/3) (AUC/week)]	100 * [Dose intensity (mg/week) / (1200 /3 (mg/week)]
Relative Dose (%)	100 * [Cumulative dose (mg/m ²) / (720 × number of cycles (mg/m ²)]	100 * [Cumulative dose (mg/m ²) / (300 × number of cycles (mg/m ²)]	100 * [Cumulative dose (AUC) / (5 × number of cycles (AUC)]	100 * [Cumulative dose (mg) / (1200 × number of cycles (mg)]

AUC = area under curve; BSA = body surface area; IV = intravenous.

*Atezolizumab will have these calculated for the induction, maintenance, and overall periods.

5.2.1.4. Modifications of Study Therapy, Including Cycle (Dose) Delay, Missed Doses, Dose Interruptions, and Dose Reductions.

- After Cycle 1, patients need to meet pre-specified laboratory parameter criteria before initiating Cycle 2 and each subsequent cycle of chemotherapy. A “Cycle Day Status” page asks if the cycle was delayed. If the start of the current cycle was delayed (the site

answers “Yes”), this will be counted as a delay. Reason for delay is not collected. Delays will be calculated over the induction, maintenance, and overall periods.

- Missed doses are identified on the dosing page of each study drug based on the question “Was the dose given?”. The missed dose information will be obtained for each study drug. For a study drug, if the last record of response to question “Was the dose given?” is No, it will not be considered as a missed dose but instead considered to be end of treatment if both criteria below are met
 - No other study drugs are given on the same day, and
 - No study drugs are given subsequently.

The reasons for missed doses will be summarized in the following categories: (1) Hematological toxicity, (2) Non-hematological toxicity, and (3) Other.

- Dose reductions are not permitted for trilaciclib or atezolizumab.
- Dose reductions for carboplatin and etoposide are determined by comparing the actual dose on the respective drug administration pages between the current cycle and the previous cycle. A window of 10% around both etoposide and carboplatin doses will be used to check for dose reductions. They occur in the following order:
 - 1st Reduction: Etoposide dose reduced from 100 mg/m² to 75 mg/m², Carboplatin dose reduced from AUC 5 to AUC 4.
 - 2nd Reduction: Etoposide dose reduced to 50 mg/m², Carboplatin dose reduced to AUC 3.

No more than 2 dose reductions of E/P in total are allowed for any patient. Toxicity that requires dose reduction more than twice will lead to discontinuation of trilaciclib or placebo + E/P therapy; discontinuations will not be counted as a dose reduction. All dose reductions for toxicity are permanent, and no dose increases are allowed when dose reductions are made for toxicity.

- Dose interruptions for all drugs are also captured on the dosing page and will be summarized for each study drug.

